8.2. Secondary Efficacy Analysis

All secondary efficacy analyses will be performed using the ITT and mITT populations, unless otherwise specified.

8.2.1. Body Investigator Global Assessment (B-IGA)

The scale, grade, and description for the B-IGA is identical to the S-IGA, as discussed in Section 8.1.

Achievement of a B-IGA score of “clear” or “almost clear” PLUS a 2-grade improvement from baseline at Weeks 2, 4, 8, and 9 will be analyzed similar to the primary efficacy endpoint using CMH test stratified by country, baseline S-IGA category, and baseline B-IGA category, with the exception that missing data will not be replaced (i.e., observed data). Odds ratios and 95% CIs of the odds ratios will be provided. Additionally, the 95% Wilson CIs for proportion of successes in each treatment group will be presented. In addition, the number and percentage of subjects in each category will be summarized by treatment and visit. Only the Week 8 results using the ITT population will be included in the testing strategy.

Analysis of change from baseline in B-IGA scores at Weeks 2, 4, 8, and 9 will be performed using descriptive summaries (mean, median, inter-quartile range) by treatment group and study visit.

8.2.2. Psoriasis Scalp Severity Index (PSSI)

The PSSI is used to measure the severity of psoriasis, combining the assessment of the severity of scalp lesions and the area of scalp affected into a single score ranging from 0 (no disease) to 72 (maximal disease). The PSSI score will be analyzed as follows:

- Change and percent change from baseline to Weeks 2, 4, 8, and 9 in the PSSI will be analyzed using descriptive summaries and an analysis of covariance (ANCOVA) with terms for country, baseline S-IGA category, and baseline B-IGA category, and baseline PSSI score as a covariate. Statistical comparisons between the treatment groups will be obtained using contrasts. The least-squares (LS) means, standard errors, 95% CIs, and *P* values will be presented.
- Frequencies and percentages of subjects achieving PSSI-50, PSSI-75, PSSI-90, and PSSI-100 will be presented by study week and treatment group. Additionally, these endpoints will be analyzed similar to the primary efficacy endpoint using a CMH test stratified by country, baseline S-IGA category, and baseline B-IGA category, on observed data. Only the PSSI-75 and PSSI-90 at Week 8 using the ITT population will be included in the testing strategy. Odds ratios and 95% CIs of the odds ratios will be provided. Additionally, the 95% Wilson CIs for proportion of successes in each treatment group will be presented.
- Time to achieving PSSI-50, PSSI-75, and PSSI-90 will be summarized using Kaplan-Meier methods and the difference between treatment groups evaluated using the log-rank statistic, and 95% CIs of the median for each treatment group will be presented. In addition, a Cox proportional hazards model that includes the stratification factors will be run and the hazard ratio and associated 95% Wald CIs will be presented. Time to achieving PSSI-50 using the ITT population will also be included in the testing strategy. Time to achieving PSSI-75 or PSSI-90 using the ITT population will not be included in the testing strategy, but will be considered as a supportive analysis.

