**Figure 3: Primary and Secondary Endpoint Testing**

Achievement of IGA success is a score of 'clear' or 'almost clear' plus a 2 grade improvement from baseline.  
Scalp WI-NRS success is a 4 point reduction in WI-NRS among subjects with WI-NRS  $\geq 4$  at baseline.  
CFB – Change from baseline

The binary secondary endpoints will be analyzed using a Cochran-Mantel-Haenszel test stratified by country, baseline S-IGA, and baseline B-IGA similar to the primary endpoint.

The continuous secondary endpoints will be analyzed using an analysis of covariance with treatment, the stratification factors including country, baseline S-IGA, and baseline B-IGA, and baseline value as independent variables. Statistical comparison between the active treatment arm and vehicle arm will be facilitated by using contrasts.

Time-to-event endpoints will be analyzed using the Kaplan-Meier estimator. Treatment group comparisons will be performed using the log-rank statistic.

Sensitivity analyses of secondary endpoints may be conducted in by study site or groups of study sites.

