3.3. Study Population

Study population consists of male and female subjects aged 12 years or older with no more than 25% BSA of scalp and body psoriasis. Subjects should have a minimum S-IGA of at least “Moderate” (3) and B-IGA of “Mild” (2) at Baseline. Note that the original protocol allowed subjects having an S-IGA of “Mild” (2) to be enrolled, and some subjects were enrolled and treated with an S-IGA of “Mild” before the amendment under which this SAP operates was put into effect (i.e., Amendment Version 1.0, dated 13-Jan-2020).

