3.5. Method of Assigning Subjects to Treatment Groups

Subjects will be randomized and assigned to active drug or vehicle will be made at a 2:1 ratio according to a computer-generated randomization list. Randomization will be stratified by country, baseline S-IGA (S-IGA=2 vs. S-IGA \geq 3), and baseline B-IGA (B-IGA=2 vs. B-IGA \geq 3).

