6.1.3. Multiple Comparisons

To control for multiple comparisons among the secondary endpoints, the following testing plan will be used, as outlined in Figure 1.

Upon demonstration of statistical significance for S-IGA Success at Week 8, the secondary endpoint of B-IGA Success at Week 8 will be tested hierarchically at the 5% significance level.

If the test for B-IGA Success at Week 8 is significant, the α of 0.05 will be split to test 2 families of secondary endpoints. The first family comprise the PSSI-75, which will be tested at the $\alpha = 0.03$ level. If the test of PSSI-75 is statistically significant, then $\alpha = 0.03$ will be used with a Holm testing procedure to test the 4 endpoints of time to success in PSSI-50, change from baseline in Total PSD score at Week 8, change from baseline in Total PSD score at Week 4, and PSSI-90 at Week 8. The remaining $\alpha = 0.02$ will be used to test the second family, comprising the SI-NRS at Week 8, the SI-NRS at Week 4, and the SI-NRS at Week 2. The tests within this second family will be hierarchical, beginning with the endpoint at Week 8, followed by Week 4 and Week 2.

Figure 1: Primary and Secondary Endpoint Testing

Achievement of IGA success is a score of “clear” or “almost clear” plus a 2-grade improvement from baseline.
 SI-WRS Success is a 4-point reduction in SI-NRS among subjects with SI-NRS ≥ 4 at baseline.
 B-IGA = Body-Investigator Global Assessment; EP = endpoint; CFB = change from baseline; PSSI = Psoriasis Scalp Severity Index; S-IGA = Scalp-Investigator Global Assessment; SI-NRS = Scalp Itch - Numeric Rating Scale.

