[1] PSSI-50 is populated with "Yes" when there is an achievement of a 50% reduction in PSSI total score from baseline; "No" otherwise.

[2] PSSI-75 is populated with "Yes" when there is an achievement of a 75% reduction in PSSI total score from baseline; "No" otherwise.

[3] PSSI-90 is populated with "Yes" when there is an achievement of a 90% reduction in PSSI total score from baseline; "No" otherwise.

[4] PSSI-100 is populated with "Yes" when there is an achievement of a 100% reduction in PSSI total score from baseline; "No" otherwise.

[5] 95% CI for "Yes" are obtained using Wilson method.

[6] The odds ratio, 95% CI, and P value are obtained from Cochran Mantel Haenszel test (stratified by country, baseline S-IGA score category, and baseline B-IGA score category) comparing roflumilast foam 0.3% to vehicle.

Reference Listings: 16.2.6.1, 16.2.6.2, 16.2.6.3

Table 14.2.3.4
Summary of Achievement of PSSI-50, PSSI-75, PSSI-90, and PSSI-100 by Study Visit
mITT Population

(Programming note: Same as table 14.2.3.3.)

Table 14.2.3.5
Time to Achievement of PSSI-50, PSSI-75, and PSSI-90
ITT Population

Variable Statistic	Roflumilast Foam 0.3% (N=XXX)	Vehicle (N=XXX)
Time to Achieve PSSI-50 (Days) [1]		
n	XXX	XXX
Events/Censors [2]	XX/XX	XX/XX
Mean (SD)	X.X (X.XX)	X.X (X.XX)
Median	X.X	X.X
Min, Max	X, XX	X, XX
Kaplan-Meier Estimate of Time to Achieve PSSI-50 (Days)		
Median (95% CI)	X.X (X.X, X.X)	X.X (X.X, X.X)
P value [3]	X.XXXX	
Cox Proportional Hazards Model [4]		
Hazard Ratio	X.XXX	
(95% Wald CI for Hazard Ratio)	(X.XXX, X.XXX)	

Repeat for “Time to Achieve PSSI-75 (Days) [5]” and “Time to Achieve PSSI-90 (Days) [6]”

Abbreviations: CI = confidence interval; NE = not estimable; PSSI = Psoriasis Scalp Severity Index; SD = standard deviation.
 Note: Subjects are summarized by planned treatment. Censored values are not included in the descriptive statistics. Only subjects who achieved PSSI-50, PSSI-75, or PSSI-90 are included in the relevant descriptive statistics.
 [1] PSSI-50 is achievement of 50% reduction in PSSI from baseline. Time to PSSI-50 is calculated as date of PSSI-50 achievement - Day 1 date + 1.
 [2] Subjects who did not achieve PSSI-50, PSSI-75, or PSSI-90 were censored at day of discontinuation or date lost to follow-up, whichever is earlier.
 [3] P value was obtained from the log rank test where roflumilast foam 0.3% was compared to vehicle.

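### The Holm-tested log-rank test for time to PSSI-50 leaves out the randomisation strata; stratifying it would be a cheap improvement

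*SAP*

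**What the plan says.** SAP 3.5 sets the design: "Randomization will be stratified by country, baseline S-IGA" (2 against 3 or more) and baseline B-IGA (2 against 3 or more).

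Time to PSSI-50 is a formally tested endpoint. SAP 8.2.2: "Time to achieving PSSI-50 using the ITT population will also be included in the testing strategy". SAP 6.1.3 says that alpha 0.03 "will be used with a Holm testing procedure to test the 4 endpoints of time to success in PSSI-50", the two PSD changes and PSSI-90.

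Three places describe the test, and none names strata:
- SAP 8.2.2: "the difference between treatment groups evaluated using the log-rank statistic".
- SAP 14.2, Table 14.2.3.5 footnote [3]: "P value was obtained from the log rank test where roflumilast foam 0.3% was compared to vehicle".
- Protocol 6.3.2, below Figure 3: "Treatment group comparisons will be performed using the log-rank statistic".

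SAP 8.2.2 then adds that "a Cox proportional hazards model that includes the stratification factors will be run". By that text and footnote [4] of the table, this model supplies a hazard ratio and Wald interval. It does not supply the tested p-value.

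**The concern.** When subjects are randomised in blocks within strata, the arms are balanced on the stratification factors by design. If those factors also affect how soon a subject reaches PSSI-50, an unstratified log-rank variance still counts differences between strata that the design has prevented from separating the arms. The variance is then too large and the test conservative. Mixing strata with different hazards also pulls the marginal treatment effect towards the null.

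Three things are at stake:
- Power for time to PSSI-50, if the factors are prognostic.
- Possible spill-over. Under Holm, an endpoint that fails to reject leaves the PSD and PSSI-90 tests on stricter thresholds, or stops the procedure before them.
- Discordant reporting. Table 14.2.3.5 shows an unadjusted p-value together with an adjusted hazard ratio and interval. The two can disagree, and the plan does not say how to read that.

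**Working it through.** **Consistency of the alpha-controlled tests**

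| Endpoint | Test | Uses the three factors? |
|---|---|---|
| S-IGA success, Week 8 (SAP 8.1.1) | CMH | Yes |
| B-IGA success, Week 8 (8.2.1) | CMH | Yes |
| PSSI-75 and PSSI-90, Week 8 (8.2.2) | CMH | Yes |
| SI-NRS, Weeks 8, 4 and 2 (8.2.3) | CMH | Yes |
| PSD change, Weeks 8 and 4 (8.2.4) | ANCOVA | Yes |
| Time to PSSI-50 (8.2.2) | Log-rank | No |

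Time to PSSI-50 is the only exception, and neither document gives a reason for it.

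**The plan's own power figure.** None exists for this endpoint. SAP 3.2 gives 96% for S-IGA success only (200 against 100 subjects, 32.2% against 9.8%, two-sided alpha 0.05). The pooled rate is (200 × 0.322 + 100 × 0.098)/300 = 0.2473. The null SE is √(0.2473 × 0.7527 × (1/200 + 1/100)) = 0.0528. The alternative SE is √(0.322 × 0.678/200 + 0.098 × 0.902/100) = 0.0444. Power is Φ((0.224 − 1.96 × 0.0528)/0.0444) = 99.7%. The stated 96% is therefore not reproduced. It is understated, which does no harm and has no bearing on this point.

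**Thresholds.** Holm over four endpoints at 0.03 gives 0.03/4 = 0.0075, 0.03/3 = 0.01, 0.03/2 = 0.015 and 0.03.

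**The two tests.** Both use Z = Σ(d₁ − d·n₁/n) / √Σ[d(n₁/n)(1 − n₁/n)(n − d)/(n − 1)], summed over visits. Here d is events, n is subjects at risk, and the subscript 1 marks the active arm. The stratified test computes the sums within each stratum and then adds them; the unstratified test treats all subjects as one stratum.

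**Simulation inputs**
- From the documents: 300 subjects, 2:1; PSSI read at Weeks 2, 4, 8 and 9; strata country × S-IGA × B-IGA; two-sided tests.
- Assumed: four countries with 45/30/15/10% of subjects; S-IGA of 2 in 10%; B-IGA of 3 or more in 75%; blocks of 3; 8% dropout; exponential times; treatment hazard ratio (HR) 1.75; baseline hazards set to give about 155 to 160 events.
- Prognostic effect (assumed): HR of 1.0, 1.2, 1.5 or 2.5 for each of S-IGA and B-IGA, with an HR between successive countries of 1.0, 1.1, 1.25 or 1.6.
- Replicates: 8,000 under the null and 5,000 under the alternative per scenario. Monte Carlo SE is about 0.2 points for type I error at 0.03 and 0.5 to 0.7 points for power.

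**Results (unstratified / stratified)**

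| Stratum effect | Type I error at 0.03 | Power at 0.03 | Power at 0.0075 |
|---|---|---|---|
| None | 3.1% / 3.2% | 84.1% / 83.3% | 67.8% / 66.0% |
| Weak (1.2) | 3.0% / 3.2% | 84.5% / 83.4% | 67.8% / 67.0% |
| Moderate (1.5) | 2.8% / 2.9% | 82.0% / 82.8% | 64.5% / 65.3% |
| Strong (2.5) | 1.7% / 2.9% | 71.6% / 80.6% | 49.1% / 64.0% |

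- None or weak: stratifying costs about 1 point at 0.03 and 1 to 2 points at 0.0075.
- Moderate: stratifying gains 82.8 − 82.0 = 0.8 points, and 65.3 − 64.5 = 0.8 points.
- Strong: stratifying gains 80.6 − 71.6 = 9.0 points, and 64.0 − 49.1 = 14.9 points.

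**Sensitivity to event count.** A second run used treatment HR 1.6 and a lower event rate, so the strong scenario had about 74 events. The pattern was the same. The strong-case gain was smaller: 27.5% to 32.1% at 0.03 (about 5 points) and 11.9% to 15.0% at 0.0075 (about 3 points).

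**The case against.** The strongest reply is that an unstratified log-rank test beside an adjusted Cox model is a prespecified choice. It matches the protocol, and a strata-adjusted estimate is reported anyway. That is fair as far as validity goes: when the strata are ignored, any error is in the conservative direction.

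A reader might infer that the p-value is bound to be conservative and that power is certainly lost. The documents do not support that. They give no event count, hazard ratio or prognostic strength for this endpoint, and with no or weak stratum effects the unstratified test is slightly ahead. Strong effects cannot be taken for granted either. B-IGA excludes the scalp, whereas PSSI-50 is a percentage reduction from the subject's own baseline scalp score. The strong scenario is demanding for country too: successive HRs of 1.6 put the extreme countries 1.6³ ≈ 4.1 apart.

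Sparse cells are a genuine cost. The protocol plans 40 to 45 sites in North America, Australia and Europe. SAP 3.3 notes that "some subjects were enrolled and treated with an S-IGA of" Mild before the amendment, so that level holds only those early subjects. A cell with one arm at risk, or with no event, adds nothing to a stratified log-rank test. However, the plan already accepts the same cells for all its CMH tests, and the simulated losses of 1 to 2 points include 16 such cells (4 × 2 × 2).

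It would also go too far to ask for the Cox model to be stratified rather than adjusted, or for time to PSSI-75, PSSI-90 or PASI-50 to change. The Cox model already includes the factors, and those endpoints are outside the testing strategy.

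**Conclusion.** The point stands as a cheap improvement, not as a correction of an invalid analysis. The omission and the inconsistency with the rest of the testing strategy are plain from the text. The effect on power is conditional:
- Strata not prognostic or weakly so: stratifying costs about 1 to 2 points.
- Moderately prognostic: it gains about 1 point at most, which is negligible.
- Strongly prognostic: it gains about 9 points at alpha 0.03 and 15 points at 0.0075 with some 155 events, and fewer points when events are scarce.

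These sizes rest on assumed country shares, stratum effects, event rates and treatment effect, none of which the documents give. They show order of magnitude only. Leaving the strata out does not inflate type I error, and the stratified test stayed close to its nominal 3%. The case for the change is a small, bounded cost against a possibly substantial gain, together with consistency across the tested endpoints.

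**What to change.** Before unblinding:
1. In SAP 8.2.2 and Table 14.2.3.5 footnote [3], state that the tested p-value for time to PSSI-50 comes from a log-rank test stratified by country, baseline S-IGA category and baseline B-IGA category.
2. Prespecify a pooling rule for sparse cells, covering small countries and the S-IGA of 2 level, to be applied without knowledge of treatment.
3. Record the change from protocol 6.3.2 in SAP section 10.
4. Keep the unstratified log-rank test as a sensitivity analysis.

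The Cox model and the other time-to-event endpoints can stay as they are. The p-value and the hazard ratio would then condition on the same factors, although they would still come from different methods.

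The cost is a sentence and a pooling rule in the SAP, a footnote, an entry in section 10 and a small programming change, with no new data. The downside is the small power loss if the strata turn out not to matter.

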8.2.3. Scalp Itch – Numeric Rating Scale (SI-NRS)

The SI-NRS scale ranges from 0 to 10 with 0 being “no scalp itch” and 10 equaling “worst scalp itch imaginable.” This will be determined by asking the subject’s assessment of worst scalp itch over the past 24 hours. The SI-NRS will be analyzed as follows:

- Change and percent change from baseline to Weeks 2, 4, and 8 in SI-NRS will be analyzed using descriptive summaries and an ANCOVA with terms for country, baseline S-IGA category, and baseline B-IGA category, and baseline SI-NRS score as a covariate. Statistical comparisons between the treatment groups will be obtained using contrasts. The LS means, standard errors, 95% CIs, and *P* values will be presented.
- In subjects with a baseline SI-NRS score ≥ 4 , achievement of a ≥ 4 -point improvement from baseline in SI-NRS score at Weeks 2, 4, and 8 will be analyzed using CMH tests stratified by country, baseline S-IGA category, and baseline B-IGA similar to the primary analysis above, with the exception that missing data will not be replaced. Odds ratios and 95% CIs of the odds ratios will be provided. Additionally, the 95% Wilson CIs for proportion of successes in each treatment group will be presented. This will be summarized using SPRU-ITT and SPRU-mITT populations.

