4.1. Introduction

Data processing, tabulation of descriptive statistics, calculation of inferential statistics, and graphical representations, will be performed primarily using SAS (release 9.4 or higher). If the use of other software is warranted for analyses conducted by Premier Research, the final statistical methodology report will detail what software was used for what purposes.

Continuous (quantitative) variable summaries will include the number of subjects (n) with nonmissing values, mean, standard deviation (SD), median, minimum, and maximum.

Categorical (qualitative) variable summaries will include the frequency and percentage of subjects who are in the particular category or each possible value. In general, the denominator for the percentage calculation will be based upon the total number of subjects in the study population for the treatment group, unless otherwise specified.

Unless otherwise indicated, all statistical tests will be conducted at the familywise $\alpha=0.05$ significance level using 2-tailed tests, and *P* values will be reported. Corresponding 95% confidence intervals (CIs) will be presented for statistical tests. Details for splitting the familywise α to control for multiple comparisons will be discussed in Section 6.1.3.

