4.2. Interim Analysis and Data Monitoring

No interim efficacy analyses are planned.

5. Analysis Populations

The following analysis populations are planned for this study:

- **Safety Population (SAF):** The Safety population will include all subjects who are enrolled and received at least 1 confirmed dose of investigational product (IP). This population will be used for all safety analyses.
- **Intent-To-Treat Population (ITT):** The ITT population will include all randomized subjects. This population will be the primary analysis population for the analysis of efficacy endpoints, along with subject disposition.
- **Modified Intent-To-Treat Population (mITT):** The mITT population includes all randomized subjects with the exception of subjects who missed the Week 8 S-IGA assessment specifically due to novel coronavirus disease-19 (COVID-19) disruptions. This population will be the sensitivity analysis population for the analysis of primary and secondary efficacy endpoints.
- **Scalp Pruritus ITT Population (SPRU4-ITT):** The SPRU4-ITT population is a subset of the ITT population and includes subjects with SI-NRS score ≥ 4 at baseline. This population will be used for the analysis of achievement of a 4-point reduction in SI-NRS score as compared to baseline for this subset of ITT subjects.
- **Scalp Pruritus mITT Population (SPRU4-mITT):** The SPRU4-mITT population is a subset of the mITT population and includes subjects with SI-NRS score ≥ 4 at baseline. This population will be used for the analysis of achievement of a 4-point reduction in SI-NRS score as compared to baseline for this subset of mITT subjects.
- **Pruritus ITT Population (PRU4-ITT):** The PRU4-ITT population is a subset of the ITT population and includes subjects with WI-NRS score ≥ 4 at baseline. This population will be used for the analysis of achievement of a 4-point reduction in WI-NRS score as compared to baseline for this subset of ITT subjects.
- **Pruritus mITT Population (PRU4-mITT):** The PRU4-mITT population is a subset of the mITT population and includes subjects with WI-NRS score ≥ 4 at baseline. This population will be used for the analysis of achievement of a 4-point reduction in WI-NRS score as compared to baseline for this subset of mITT subjects.

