Abbreviations: B-IGA = body investigator global assessment; CI = confidence interval; S-IGA = scalp investigator global assessment; SI-NRS = Scalp Itch – Numeric Rating Scale.

Note: Percentages are n/Number of subjects in the SPRU4-ITT population within planned treatment at each visit*100. Baseline is the last non-missing measurement taken on or before the day first application of study drug.

[1] SI-NRS success (“Yes”) is defined as an achievement of a ≥ 4 -point improvement from baseline score of ≥ 4 ; “No” otherwise.

[2] 95% CIs for “Yes” are obtained using Wilson method.

[3] The odds ratio, 95% CI, and P value are obtained from Cochran Mantel Haenszel test (stratified by country, baseline S-IGA score category, and baseline B-IGA score category) comparing roflumilast foam 0.3% to vehicle.

Reference Listings: 16.2.6.1, 16.2.6.2, 16.2.6.4

Table 14.2.4.4

Scalp Itch – Numeric Rating Scale (SI-NRS) Pruritus Score Success by Study Visit
mITT Population, Subjects with SI-NRS Pruritus Score ≥ 4 at Baseline (SPRU4-mITT Population)

(Programming note: Same as table 14.2.4.3. Change “Note:” to be “Note: Percentages are n/Number of subjects in the SPRU4-mITT population within planned treatment at each visit*100.”)

Table 14.2.4.5

Summary of Scalp Itch – Numeric Rating Scale (SI-NRS) Pruritus Score by Study Visit – ANCOVA
ITT Population

(Programming note: Same as table 14.2.3.7. Update [1] as to use “SI-NRS score” instead of “PSSI score”. Update abbreviation row to display “SI-NRS = Scalp Itch – Numeric Rating Scale”. Change reference listing to Reference Listings: 16.2.6.1, 16.2.6.2, 16.2.6.4. Update the Note as “Note: Subjects are summarized by planned treatment. The SI-NRS will be determined by asking the subject’s assessment of worst itch of scalp over the past 24 hours. The scale is from 0 to 10, which ranges from “no scalp itch” to “worst scalp itch imaginable”. Baseline is the last non-missing measurement taken on or before the day of first application of study drug. Percent change from baseline is calculated as (result – baseline result)*100.”)

Table 14.2.4.6

Summary of Scalp Itch – Numeric Rating Scale (SI-NRS) Pruritus Score by Study Visit – ANCOVA
mITT Population

(Programming note: Same as table 14.2.4.5.)

Table 14.2.5.1
Summary and Change from Baseline in Psoriasis Symptom Diary (PSD) Total and Individual Item Scores by Study Visit
ITT Population

(Programming note: Same as table 14.2.3.1, except add header rows at the top for

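### The three alpha-controlled scalp-itch responder tests leave out baseline SI-NRS; the planned CMH test is valid but probably loses some power at alpha 0.02

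*SAP*

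**What the plan says.** The tested itch endpoints are responder endpoints. SAP 6.1.3 sets up a second secondary family "comprising the SI-NRS at Week 8, the SI-NRS at Week 4, and the SI-NRS at Week 2", opened only after S-IGA and B-IGA success. On level: "The remaining $\alpha = 0.02$ will be used to test the second family". On order: "The tests within this second family will be hierarchical, beginning with the endpoint at Week 8, followed by Week 4 and Week 2". SAP 4.1 makes tests two-sided ("significance level using 2-tailed tests"). The analysis set in SAP section 5 "includes subjects with SI-NRS score ≥ 4 at baseline".

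SAP 8.2.3 says that the response "will be analyzed using CMH tests stratified by country, baseline S-IGA category, and baseline B-IGA similar to the primary analysis above". Footnote [3] of Table 14.2.4.3 repeats this: results are "obtained from Cochran Mantel Haenszel test (stratified by country, baseline S-IGA score category, and baseline B-IGA score category"). Protocol 6.3.2 gives the same strata for all binary secondary endpoints. None of these places has a baseline SI-NRS term.

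The preceding bullet of SAP 8.2.3 analyses change in SI-NRS by ANCOVA with the same factors "and baseline SI-NRS score as a covariate". That analysis is outside the testing strategy.

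Neither document gives SI-NRS response rates, the share of subjects entering at 4 or more, or power for this family. Protocol 6.5.1 uses an entry score of 6 for this endpoint where every other place uses 4. That needs reconciling; I take 4.

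**The concern.** The endpoint is an absolute drop of 4 points on a 0 to 10 scale. A subject entering at 4 must reach 0; a subject entering at 10 need only reach 6. Baseline itch therefore probably affects the chance of response in both arms. It is not a randomization factor (SAP 3.5), so chance imbalance between the arms is not adjusted for in the tests that count.

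The family has only alpha 0.02, and a miss at Week 8 closes Weeks 4 and 2. Power lost at Week 8 is lost for all three claims. The authors already treat baseline SI-NRS as worth adjusting for in the untested analysis.

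**Working it through.** **1. The plan's own power figure.** It concerns S-IGA only: 200 vs 100 subjects, 32.2% vs 9.8%, two-sided alpha 0.05, stated power 96%. Pooled rate = (64.4 + 9.8)/300 = 0.2473. Null SE = √(0.2473 × 0.7527 × 0.015) = 0.0528; alternative SE = √(0.322 × 0.678/200 + 0.098 × 0.902/100) = 0.0444. Power = Φ((0.224 − 1.96 × 0.0528)/0.0444) = 99.7%. The stated 96% is not reproduced, but it is conservative and does not bear on the itch tests.

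**2. The itch test before any covariate.** Assumed: 80% of 300 enter at 4 or more (160 active, 80 vehicle), with response 50% vs 30%. Pooled rate = (80 + 24)/240 = 0.4333; null SE = 0.0679; alternative SE = 0.0647. Power = Φ((0.20 − 2.326 × 0.0679)/0.0647) = 74% at alpha 0.02, against 85% at 0.05. Under these assumptions, a few points matter.

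**3. How baseline b may enter.** Suppose the drop is normal on an underlying scale and counts as 4 points when it rounds to 4 (at least 3.5).
- Drop averaging half of baseline: P = Φ((0.5b − 3.5)/SD). With SD 3, this is 31% at b = 4 and 69% at b = 10; with SD 2, 23% and 77%. The logit slope per point is [logit(0.69) − logit(0.31)]/6 = 0.27 for SD 3 and 0.41 for SD 2.
- Drop averaging a fixed m points: P = Φ((m − 3.5)/SD). Baseline disappears and the slope is 0.

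**4. Planned CMH against logistic regression.** The logistic model is a likelihood ratio test with the stratification factors as main effects and SI-NRS linear. Assumed: 2:1 allocation; baseline scores 4 to 10 with weights 10, 13, 15, 20, 20, 12 and 10%; three countries (60/25/15%); 90% with S-IGA ≥3; 70% with B-IGA ≥3; baseline itch independent of these factors. Two-sided alpha 0.02, 2,500 trials per cell. Entries are power in %, CMH → logistic.

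| Logit slope per point | N=180, 30% vs 50% | N=240, 30% vs 50% | N=270, 30% vs 50% | N=240, 35% vs 60% |
|---|---|---|---|---|
| 0 | 54.0 → 57.5 | 72.2 → 75.8 | 77.8 → 80.2 | 89.6 → 90.6 |
| 0.15 | 58.1 → 63.0 | 73.8 → 78.2 | 77.6 → 80.2 | 89.1 → 90.8 |
| 0.3 | 55.9 → 62.8 | 72.3 → 78.0 | 77.5 → 82.6 | 88.8 → 92.1 |
| 0.5 | 57.8 → 69.1 | 72.8 → 81.9 | 79.6 → 87.0 | 89.4 → 95.3 |

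Part of each gain is not due to baseline itch: at slope 0 the logistic model already gains 1.0 to 3.6 points, presumably because main effects are cheaper than 3 × 2 × 2 = 12 crossed strata. Subtracting the slope-0 gain leaves, for baseline itself, 0.2 to 1.4 points at slope 0.15, 2.1 to 3.4 at 0.3 and 4.9 to 7.8 at 0.5. The Monte Carlo SE per cell is about √(0.73 × 0.27/2500) = 0.9 points, so differences near 1 point are noise. In a null run (slope 0.3, 35% in both arms, 6,000 trials), both tests rejected 2.3% of the time.

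**5. Two other sets of runs, N=240.**
- Follow-up score regressed on baseline with coefficient ρ (SD 2.0 or 2.5). The slope is 0 at ρ = 1, 0.20 to 0.25 at 0.7, 0.34 to 0.42 at 0.5 and 0.48 to 0.60 at 0.3. Against a logistic model without baseline, the gain from baseline itself was about 1 to 2, 4 and 5 to 8 points at ρ = 0.7, 0.5 and 0.3.
- Two or four countries: logistic against planned CMH gained about 1 to 10 points in total, of which about 0 to 9 came from baseline. Null rejection was 2.1 to 2.4%.

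**6. SI-NRS groups (4–5, 6–7, 8–10) as extra CMH strata, N=240.** With three countries, 12 strata become 36, or 240/36 = 6.7 subjects per stratum, about 2.2 of them on vehicle. If itch falls proportionally (60% vs 42%), power moved from 86.1% to 91.6% in the best case (one country, residual SD 0.25) and from 40.6% to 38.4% in the worst (five countries, SD 0.45). If itch falls by a fixed number of points (4.3 vs 3.0), power fell in every case: by 1 to 2 points with one country, 2.5 to 4 with three and 4.5 to 6 with five.

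**The case against.** The planned test is valid: randomization protects it, and its null rejection was 2.0 to 2.3% against a nominal 2%. It matches Protocol 6.3.2 and the tests of B-IGA, PSSI-75 and PSSI-90. Baseline SI-NRS is tabulated by arm (SAP 7.3), and the ANCOVA gives a baseline-adjusted view of the same scale. The gain rests on a relation between baseline and response that the documents do not report; if itch falls by a fixed number of points, there is nothing to gain.

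All of that stands, and it limits the point to efficiency. It does not remove it. A fixed-point fall needs the follow-up score to track baseline one for one, which is unlikely in a set selected for a high value on a single 24-hour recall item. The ANCOVA cannot rescue a missed Week 8 test, because it is outside the testing strategy.

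A reader might infer that baseline decides whether a 4-point drop is possible at all. The documents do not support that: everyone in the set enters at 4 or more, so everyone can respond, and only the probability can vary. A reader might also take the obvious remedy to be more CMH strata; step 6 shows that this can cost as much as it gains.

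**Conclusion.** The omission is real and confined to the three tests that count. It is an efficiency loss, not a validity error. Baseline itself is worth about 0 to 9 points of power at alpha 0.02, depending on how prognostic baseline itch is. Slopes of roughly 0.27 to 0.41, which follow if itch falls by about half, put the gain at a few points. These figures rest on assumed response rates, an assumed 60 to 90% of subjects entering at 4 or more, and an assumed country mix; none is in the documents. It would overstate the case to say that the itch family is underpowered because of this choice, since no SI-NRS rates are given from which to judge.

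**What to change.** Before unblinding, amend SAP 8.2.3 and Tables 14.2.4.3 and 14.2.4.4:
- Make the test at Weeks 8, 4 and 2 a logistic regression with treatment, country, baseline S-IGA category, baseline B-IGA category and continuous baseline SI-NRS. Use a two-sided likelihood ratio test of treatment at 0.02 in the existing sequence.
- Keep the planned CMH as a supportive analysis.
- Record the departure from Protocol 6.3.2 in SAP section 10.

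Do not add SI-NRS groups to the CMH strata. Do not leave the method to an undefined judgement that strata are too sparse, which would choose an alpha-controlled test after seeing the data.

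The cost is SAP wording and two table footnotes; baseline SI-NRS is already collected. The downside is small: the tested odds ratio becomes conditional on baseline itch, and the method differs from that of the other binary endpoints.
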